#### **Treatment grouping 1 (TG1) for Placebo controlled period from Day 1 to Week 26:**

- *Placebo (Pbo)*
- *Linagliptin 5 mg (L5)*
- *Empagliflozin pooled (E Pooled)*, consisting of
  - Empagliflozin 10 mg responders at Week 12 to 10 mg (E10R-10)
  - Empagliflozin 10 mg non-responders at Week 12 to 10 mg (E10NR-10)
  - Empagliflozin 10 mg non-responders at Week 12 to 25 mg (E10NR-25)
  - Empagliflozin 10 mg and not proceed to re-randomisation at Week 14 (E10)

**Treatment grouping 2 (TG2) for Empagliflozin 25 mg titration period from Day 1 to Week 26:**

- *Placebo (Pbo)*
- *Empagliflozin titration start with 10 mg and increased dose at re-randomisation if needed (E Titr25)*, consisting of
  - Empagliflozin 10 mg responders at Week 12 to 10 mg (E10R-10)
  - Empagliflozin 10 mg non-responders at Week 12 to 25 mg (E10NR-25)
  - Empagliflozin 10 mg and not proceed to re-randomisation at Week 14 (E10)

**Treatment grouping 3 (TG3) for Empagliflozin 10 mg titration period from Day 1 to Week 26:**

- *Placebo (Pbo)*
- *Empagliflozin titration start with 10 mg and dose remained at re-randomisation if needed (E Titr10)*, consisting of
  - Empagliflozin 10 mg responders at Week 12 to 10 mg (E10R-10)
  - Empagliflozin 10 mg non-responders at Week 12 to 10 mg (E10NR-10)
  - Empagliflozin 10 mg and not proceed to re-randomisation at Week 14 (E10)

**Treatment grouping 4 (TG4) for the period following the administration of the re-randomised medication planned at Week 14 up to Week 26/Week 52:**

- *Empagliflozin 10 mg after initial Empagliflozin 10 mg non-response (E10NR/10\*)*
- *Empagliflozin 25 mg after initial Empagliflozin 10 mg non-response (E10NR/25\*)*

**Treatment grouping 5 (TG5) for long term analysis period from Day 1 to Week 52:**

- *Linagliptin 5 mg (L5)*
- *Empagliflozin pooled (E Pooled)*, consisting of
  - Empagliflozin 10 mg responders at Week 12 to 10 mg (E10R-10)
  - Empagliflozin 10 mg non-responders at Week 12 to 10 mg (E10NR-10)
  - Empagliflozin 10 mg non-responders at Week 12 to 25 mg (E10NR-25)
  - Empagliflozin 10 mg and not proceed to re-randomisation at Week 14 (E10)

**Treatment grouping 6 (TG6) for active treatment period:**

- *Linagliptin 5 mg active pooled (L5 active)*, consisting of
  - Linagliptin 5 mg from the initial randomisation (L5)
  - Linagliptin 5 mg after initial placebo (P/L5\*)
- *Empagliflozin active pooled (E active)*, consisting of
  - Empagliflozin 10 mg responders at Week 12 to 10 mg (E10R-10)
  - Empagliflozin 10 mg non-responders at Week 12 to 10 mg (E10NR-10)
  - Empagliflozin 10 mg non-responders at Week 12 to 25 mg (E10NR-25)
  - Empagliflozin 10 mg and not proceed to re-randomisation at Week 14 (E10)
  - Empagliflozin 10 mg after initial placebo (P/E10\*)
  - Empagliflozin 25 mg after initial placebo (P/E25\*)

**Treatment grouping 7 (TG7) for the period following the administration of the re-randomised medication planned at Week 26 up to Week 52:**

- *Linagliptin 5 mg after initial placebo (P/L5\*)*
- *Empagliflozin 10 mg after initial placebo (P/E10\*)*
- *Empagliflozin 25 mg after initial placebo (P/E25\*)*

**Treatment grouping 8 (TG8) for result disclosure from Day 1 to Week 52:**

- *Placebo and not proceed to re-randomisation at Week 26 (Pbo)*
- *Placebo to empagliflozin 10 mg at Week 26 (P-E10)*
- *Placebo to empagliflozin 25 mg at Week 26 (P-E25)*
- *Placebo to linagliptin 5 mg at Week 26 (P-L5)*
- *Linagliptin 5 mg (L5)*
- *Empagliflozin 10 mg (E10)* consisting of
  - Empagliflozin 10 mg responders at Week 12 to 10 mg (E10R-10)
  - Empagliflozin 10 mg non-responders at Week 12 to 10 mg (E10NR-10)
  - Empagliflozin 10 mg and not proceed to re-randomisation at Week 14 (E10)
- *Empagliflozin 10 mg non-responders at Week 12 to 25 mg (E10NR-25)*

**Treatment grouping 9 (TG9) for AE result disclosure from Day 1 to Week 52:**

- *Placebo before re-randomisation at Week 26 (Pbo)*
- *Linagliptin 5 mg active pooled (L5 active)*, consisting of
  - Linagliptin 5 mg from the initial randomisation (L5)
  - Linagliptin 5 mg after initial placebo (P/L5\*)
- *Empagliflozin 10 mg active pooled (E10 active)*, consisting of
  - Empagliflozin 10 mg and not proceed to re-randomisation at Week 14 (E10)
  - Empagliflozin 10 mg responders at Week 12 to 10 mg (E10R-10)
  - Empagliflozin 10 mg non-responders at Week 12 to 10 mg (E10NR-10)
  - Empagliflozin 10 mg non-responders at Week 12 before re-randomisation to 25 mg (E10NR\*/25)
  - Empagliflozin 10 mg after initial placebo (P/E10\*)

- *Empagliflozin 25 mg active pooled (E25 active)*, consisting of
  - Empagliflozin 25 mg after initial Empagliflozin 10 mg non-response (E10NR/25\*)
  - Empagliflozin 25 mg after initial placebo (P/E25\*)

The treatment grouping TGx will be used according to the type of analysis, that has been assigned for each analysis throughout the TSAP. The treatment (or a combination of treatments) with the solid bullet point will be used in the analyses and the outputs presentation will use the short name as shown in bold in brackets. Each combination of treatments is defined by a list of treatments identifying the type and timing of the treatment. As a first example, the treatment identifier “E10R-10” means the patient was initially assigned to empagliflozin 10 mg and then carried on to empagliflozin 10 mg as a responder at Week 12, the entire treatment period is included. As a second example, the treatment identifier “E10NR/25\*” means the patient was initially assigned to empagliflozin 10 mg and then carried on to empagliflozin 25 mg as a non-responder at Week 12, but only the re-randomised treatment period from Week 14 is included.

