#### 7.8.1.3 AE summaries

An overall summary of adverse events will be presented by TG1, TG6, TG5 and TG4.

The frequency of patients with adverse events will be summarised by treatment, primary system organ class and preferred term. AEs will also be reported by intensity. Separate tables will be provided for patients with other significant adverse events according to ICH E3 (6), for patients with serious adverse events, for patients with AEs leading to discontinuation, for patients with drug-related AEs and for patients with selected AESIs and other specific AEs. Incidence rate as defined in [Section 7.8.1.8](#) will apply to frequency tables: overall summary of AEs, patients with AEs, patients with drug-related AEs, patients with other significant AEs according to ICH E3, patients with AEs leading to discontinuation and patients with SAEs. All above mentioned tables will be repeated by TG1, TG6, TG5 and TG4.

The system organ classes will be sorted in descending order of the total frequency count of all treatments then followed by preferred terms in descending order of the total frequency count. Alphabetical ordering will be used for the same total frequency counts on PT level.

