Appendix 16.1.13 will include the following analyses by TG1 and TG6:

- Frequency of patients with AEs by SOC and preferred term
- Frequency of patients with SAEs by SOC and preferred term
- Frequency of patients with drug related serious AEs by SOC and preferred term
- Frequency of patients with adverse events by outcome, SOC and preferred term

Additionally, the following analyses will also be reported in Appendix 16.1.13 for disclosure on [clinicaltrials.gov](#) and [EudraCT](#):

- Frequency of patients with non-serious adverse events occurring with an incidence in preferred term greater than 5% by treatment, SOC and PT for disclosure on [clinicaltrials.gov](#).
- Frequency of patients with serious adverse events by treatment, SOC and PT for disclosure on [clinicaltrials.gov](#)
- AEs per treatment arm for disclosure on [EudraCT](#) (Number of patients exposed, affected by SAEs, affected by non-serious AEs with incidence > 5% in any treatment arm for each PT, number of death of all causes, number of deaths resulting from AEs will be presented.)

- Non-serious AEs with incidence > 5% in any treatment arm for each preferred term (grouped by standard SOC terms) for disclosure on EudraCT (Number of patients affected, exposed, total occurrences will be presented.)
- Serious AEs on preferred term (grouped by standard SOC terms) for disclosure on EudraCT (Number of patients affected, exposed, number of occurrences, occurrences causality related, fatalities, fatalities causally related to treatment will be presented.)

These result disclosure AE analyses in Appendix 16.1.13 will be performed using treatment grouping 9 for both DINAMO and DINAMO Mono together. See [\(13\)](#) for details.

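### The registry adverse-event tables set a placebo column of about 26 weeks beside active columns with longer follow-up, as crude percentages, so active columns (chiefly linagliptin) can look worse through follow-up length alone

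*SAP*

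**What the plan says.** SAP section 6.1 sets up "Treatment grouping 9 (TG9) for AE result disclosure from Day 1 to Week 52". Its four columns cover different periods:

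- **Placebo:** "Placebo before re-randomisation at Week 26 (Pbo", so at most about 26 weeks per patient.
- **Linagliptin:** the initial linagliptin arm (up to 52 weeks) plus placebo patients switched at Week 26 (about 26 weeks).
- **Empagliflozin 10 mg:** patients who stay on 10 mg (up to 52 weeks), placebo switchers (about 26 weeks), and the first 14 weeks of those later moved to 25 mg.
- **Empagliflozin 25 mg:** Week 14 to Week 52 for re-randomised non-responders (about 38 weeks) plus placebo switchers (about 26 weeks).

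Section 7.8.1.3 states: "These result disclosure AE analyses in Appendix 16.1.13 will be performed using treatment grouping 9 for both DINAMO and DINAMO Mono together". The listed content is patients affected, patients exposed, occurrences and fatalities. One display rule is "Non-serious AEs with incidence > 5% in any treatment arm for each preferred term". Incidence rates are specified in the same section for other groupings: "All above mentioned tables will be repeated by TG1, TG6, TG5 and TG4". Table 6.3:1 gives incidence rates for TG1 and TG5. TG9 is named in neither place.

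Elsewhere the SAP keeps the two time frames apart. In section 7.8 the comparison with placebo uses TG1 up to Week 26. The analyses to Week 52 (TG5, TG6) have no placebo column.

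**The concern.** A crude percentage with at least one event rises with the time over which a patient is observed. When one column is observed for 26 weeks and its neighbour for 45, the second shows a higher percentage even if the drugs do nothing. A reader of the public tables of this paediatric trial could take that gap for harm. The active columns also differ from one another in follow-up, so linagliptin, 10 mg and 25 mg are not directly comparable either. The 5% filter works on the same crude percentages, so a non-serious term can be listed because one column was followed longer.

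**Working it through.** The documents give no exposure or incidence for TG9, so there is no figure to reproduce. Expected follow-up can be built from the plan.

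**Inputs from the documents.** Initial allocation is 1:1:1. Non-responders on empagliflozin are re-randomised 1:1 at Week 14, and placebo patients 1:1:1 at Week 26 (protocol section 4.1.3). There are 50 patients per arm in the main study and about 6 in DINAMO Mono (protocol synopsis). I use 50; about 57 per arm gives the same percentages.

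**Assumptions.** Everyone completes; the hazard is constant and equal in all columns (no drug effect); the Week 12 non-responder share q lies between 0.3 and 1.0.

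**Mean follow-up per column** (50/3 = 16.7 placebo switchers to each active treatment):

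- Placebo: 26 weeks.
- Linagliptin: (50×52 + 16.7×26)/66.7 = 3033/66.7 = 45.5 weeks. Of this person-time, 50×26/3033 = 43% lies after Week 26 in the initial arm.
- 10 mg: [50(1−q/2)×52 + 50(q/2)×14 + 16.7×26]/66.7. With q = 0.3, (2210 + 105 + 433)/66.7 = 41.2. With q = 1, (1300 + 350 + 433)/66.7 = about 31.
- 25 mg: [50(q/2)×38 + 16.7×26]/[50(q/2) + 16.7]. With q = 0.3, 718/24.2 = 29.7. With q = 1, 1383/41.7 = 33.2.

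**Crude percentage under no drug effect.** If a share p has the event by Week 26, the share by t weeks is 1 − (1−p)^(t/26). Each column is the average over its components, weighted by patients. For p = 5% the component values are 2.7% (14 weeks), 5.0% (26), 7.2% (38) and 9.75% (52). Linagliptin is then 0.75×9.75% + 0.25×5% = 8.6%. For p = 10% it is 0.75×19% + 0.25×10% = 16.75%.

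| Column | Mean weeks | p = 5% | p = 10% |
|---|---|---|---|
| Placebo | 26 | 5.0% | 10.0% |
| Linagliptin | 45.5 | 8.6% | 16.75% |
| Empagliflozin 10 mg | 31–41 | 5.9–7.8% | 11.7–15.2% |
| Empagliflozin 25 mg | 30–33 | 5.7–6.3% | 11.3–12.6% |

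**Filter.** A term at 3% by Week 26 on every treatment gives 0.75×5.91% + 0.25×3% = 5.2% on linagliptin. It passes the 5% rule because of follow-up alone.

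**Check of the remedies.** Restricting all arms to Day 1 to Week 26 gives 5% in each. First events per 100 patient-years, with time counted within the column's own treatment, also agree: 100 × −ln(0.95) × 52.18/26 = 10.3 in all four columns.

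**Time at risk.** SAP section 7.8.1.8 starts time at risk at the first initially randomised dose. Applied to TG9 unchanged, it would credit each completing 25 mg patient with about 52 weeks instead of the 30 to 33 spent in that column, before any truncation at a first event.

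**The case against.** The strongest reply is that TG9 is labelled for disclosure and not as a comparison with placebo. The comparison is assigned to TG1 with equal windows (protocol section 7.3.6, SAP section 7.8). Safety analysis is descriptive, and no test rests on TG9. TG1 and TG6 tables, including adverse events and serious adverse events by preferred term, are already planned for the report and Appendix 16.1.13, and section 7.8.1.3 specifies incidence rates by TG1 and TG6. All of this stands and confines the point to the registry tables.

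The SAP also refers to an internal guide on disclosure tables that is not available here. It may require a time frame per group, and the TG9 labels already state part of the timing. A label would disclose the imbalance, but it would not equalise the percentages or the filter.

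The filter applies only to non-serious events, and longer windows can only bring more terms in. That is correct; no serious event is hidden.

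A reader might infer that every active column will show more affected patients than placebo. The plan does not support that as a count. At q = 0.7 and p = 10%, the 25 mg column expects 4.2 of 34 patients against 5.0 of 50 on placebo. Even the percentage can reverse for very common events: the 10 mg column falls below placebo when more than about 67% have the event by Week 26 if all are non-responders, or about 87% if 70% are. A reader might also infer that the trial's safety comparison with placebo is biased. It is not, because TG1 ends at Week 26 in every arm.

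**Conclusion.** The point holds for the registry tables only. Follow-up length alone would multiply an uncommon event's percentage, relative to placebo, by about 1.7 for linagliptin, 1.2 to 1.6 for empagliflozin 10 mg and 1.1 to 1.3 for 25 mg. The excess is in the percentage of patients exposed and is chiefly a linagliptin effect.

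The unequal windows and the absence of person-time come from the SAP text; the sizes rest on the assumptions above. Events concentrated early would shrink the gap, and discontinuation would change the person-time. Adding the 7-day residual period changes little: at p = 10% and q = 0.7 the active columns become 17.1%, 13.5% and 12.5%. No confirmatory result and no in-report safety comparison is affected, so this is a desirable improvement and not a serious defect.

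**What to change.** Amend SAP section 6.1 (TG9) and section 7.8.1.3 in one of two ways.

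1. **Preferred: two disclosure sets.** Take the placebo comparison from TG1, from Day 1 to the Visit 5 cut-off already defined in section 7.8.1.1. Report the active-treatment data to Week 52 by dose as a separate set with no placebo column. Apply the 5% filter within each set and state the time frame of each group.
2. **Alternative: keep TG9.** Add patient-years and first-event rates per 100 patient-years for each column.

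Wherever time at risk is used, count it from the first dose of that column's treatment and end it at the switch to another. The definition in section 7.8.1.8 cannot be carried over unchanged. Section 7.7 already uses first active intake for exposure under TG6.

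The cost is SAP wording and a re-run of planned programs, with DINAMO and DINAMO Mono combined because the disclosure tables pool them. No new data are needed, and section 7 schedules these outputs only for the final reporting. The first option means more reporting groups. Active-arm events before Week 26 would appear in both sets, and the placebo-controlled set would show empagliflozin pooled, with the dose split only in the active set.

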## 6.2 IMPORTANT PROTOCOL DEVIATIONS

A protocol deviation (PD) is important if it affects the rights or safety of the study patients, or if it can potentially influence the primary outcome measurement for the respective patients in a way that is neither negligible nor in accordance with the study objectives. The specification and handling of PDs that are determined to be important will be documented in 4-12-01-sdtm-dv-domain-specification located in BIRDS. Not all important PDs will generate exclusion from an analysis population set. The specifications will indicate which important PDs will lead to an exclusion.

The specification document will also list the PDs that have been manually evaluated and determined to be important, and confirmed at the final report planning meeting.

The impact of COVID-19 on important PDs and other COVID-19 related PDs will be also captured.

## 6.3 PATIENT SETS ANALYSED

### Screened set (SCR):

This patient set includes all patients screened for the trial, with informed consent given.

### Randomised set (RS):

This patient set includes all patients from the screened set who were randomised to study drug, regardless of whether any study drug was taken.

### Treated set (TS):

This patient set includes all patients who are treated with at least one dose of randomised study medication. The TS is the basis for safety analyses.

Treated set active (TSactive):

The TSactive is defined as all patients treated with at least one dose of active randomised study medication (linagliptin or empagliflozin) at any time in the study.

Modified Intention-to-Treat Set (mITT):

This patient set includes all randomised patients who are treated with at least one dose of study medication and have a baseline HbA1c measurement. The mITT is the basis for the primary analyses.

Per protocol set (PPS):

This patient set includes all patients in the mITT set who do not have any important PD which can be expected to have a distorting influence on the assessment of the primary endpoint. As the DINAMO primary endpoint is analysed after 26 weeks of study treatment, important PDs related to efficacy that occur after the assessment of the DINAMO primary endpoint measurement will not lead to exclusion from analysis sets. See [Section 6.2](#) for details.

PK parameter analysis set (PKS):

The pharmacokinetic set consists of all treated patients who have at least one evaluable PK plasma concentration measurement.

Table 6.3: 1 Patient sets analysed and treatment groupings

Class of endpoint	Patient sets					
	SCR	TS	TSactive	RS	mITT	PPS
Disposition	OR (TG1)	OR (TG4, TG7)	OR (TG6)	OR  (TG8)		
Definition of analysis sets			(TG6)	(TG1)		
Important protocol deviations				(TG1)		
Demographics		OR (TG1)		OR  (TG8)		
Baseline efficacy variables		OR (TG1)				
Background antidiabetic therapy at baseline		OR (TG1)				
Antidiabetic medication newly introduced on treatment		OR (TG1, TG5)				
Relevant medical history		OR (TG1)				
Exposure to study medication		OR (TG1)	OR (TG6)			
Compliance data by visit		OR (TG1)	OR (TG6)			

Table 6.3: 1 Patient sets analysed and treatment groupings (continued)

Class of endpoint	Patient sets					
	SCR	TS	TSactive	RS	mITT	PPS
DINAMO - Primary efficacy endpoint						
Primary family of hypothesis - HbA1c [%] CFB - ANCOVA analysis - washout approach					OC-AD (TG1)	
Secondary family of hypothesis - HbA1c [%] CFB - ANCOVA analysis - washout and inverse probability weighting approach					OC-AD (TG2, TG3)	
DINAMO Mono - Primary efficacy endpoint						
Occurrence of treatment failure up to or at Week 26 (DINAMO Mono patients only)					NCF (TG1)	

Table 6.3: 1 Patient sets analysed and treatment groupings (continued)

Class of endpoint	Patient sets					
	SCR	TS	TSactive	RS	mITT	PPS
Secondary efficacy endpoints						
Change in FPG [mg/dl] from baseline - ANCOVA					OC-AD-BOCF; OC (TG1)	
Change in body weight [kg] / SBP [mmHg] / DBP [mmHg] from baseline – MMRM					OC-AD; OC (TG1)	
Proportion of patients who achieve HbA1c goals < 6.5% and < 7.0%. Exact CI					NCF; OC (TG1)	

Table 6.3: 1 Patient sets analysed and treatment groupings (continued)

Class of endpoint	Patient sets					
	SCR	TS	TSactive	RS	mITT	PPS
Further safety endpoints						
Shift tables for the Tanner staging score from baseline		OC-AD (TG1, TG5)				
Descriptive statistics over time for growth velocity		OC-AD (TG1, TG5)				
Safety evaluation						
Overall summary of AEs		TG1, TG5, TG4	TG6			
Freq. of patients with the following AEs by treatment, SOC and PT 
 
• AEs
 
• AEs by worst intensity
 
• Drug-related AEs
 
• AEs leading to treatment discontinuation
 
• SAEs
 
• Other significant adverse events
 
• AESIs(except DKA and lower limb amputation)
 
		TG1, TG5, TG4	TG6			
Incidence rate of patients with AEs by treatment, SOC and PT		TG1, TG5				
List of patients with AESIs/other significant AE 
 
• DKA
 
• Events involving lower limb amputation
 
• Bone fracture
 
		TS				
Freq. of patients with other specific AE by treatment, SOC and PT: 
 
• Hypoglycaemic AE
 
• UTI (also investigator assessment, serious and leading to treatment discontinuation)
 
• Genital infection (also investigator assessment, serious and leading to treatment discontinuation)
 
• Acute pyelonephritis or urosepsis
 
• Volume depletion
 
• Ketone measurements
 
		TG1, TG4	TG6			

Table 6.3: 1 Patient sets analysed and treatment groupings (continued)

Class of endpoint	Patient sets					
	SCR	TS	TSactive	RS	mITT	PPS
Freq. of patients with other specific AE by treatment, SOC and PT: 
 
• Arthralgia
 
• Pemphigoid in bullous conditions)
 
		TG1	TG6			
Freq. of patients by characteristics of hypoglycaemia 
 
• reported AE
 
• any hypoglycaemia
 
 Freq. of patients with symptomatic hypoglycaemia AE with plasma glucose < 54 mg/dL (< 3.0 mmol/L) and/or severe hypoglycaemia AE by age at randomisation in categories.		TG1, TG4	TG6			
Number of any hypoglycaemia – time at risk						
Freq. of patients with the following events (investigator assessment) by characteristics of events 
 
• UTI
 
• Genital infection
 
• Acute pyelonephritis or urosepsis
 
 Freq. of patients with genital infection (investigator assessment) by type of the genital infection		TG1, TG4	TG6			
Freq. of patients with CEC adjudicated events		TG1	TG6			
Freq. of patients with the following AEs by SOC and PT 
 
• AEs
 
• AEs by outcome
 
• SAEs
 
• Drug-related SAEs
 
		TG1	TG6			
Freq. of patients with AEs by treatment, SOC and PT 
 
• Non-serious AE with an incidence in preferred term greater than 5%
 
• SAE
 
		TG9 				

Table 6.3: 1 Patient sets analysed and treatment groupings (continued)

Class of endpoint	Patient sets					
	SCR	TS	TSactive	RS	mITT	PPS
AEs per treatment arm (including number of patients exposed, affected by SAEs, affected by non-serious AEs with incidence > 5% in any treatment arm for each PT, number of death of all causes, number of deaths resulting from AEs).		TG9 				
Non-serious AEs with incidence > 5% in any treatment arm for each preferred term (including number of patients affected, exposed, total occurrences.)		TG9 				
SAEs on PT (including number of patients affected, exposed, number of occurrences, occurrences causality related, fatalities, fatalities causally related to treatment.)		TG9 				
Clinical laboratory evaluation						
Descriptive statistics of laboratory values at baseline, last value on-treatment, and change from baseline to last value on-treatment (normalised value) and over time		TG1, TG5				
Freq. of patients within and outside the reference range at baseline and last value on treatment.						
Freq. of patients of categorical laboratory parameters at baseline and last value on-treatment						
Freq. of patients with possibly clinical significant abnormality (PCSA)		TG1, TG5, TG4	TG6			
Freq. of patients with elevated liver enzymes		TG1, TG5	TG6			

Table 6.3: 1 Patient sets analysed and treatment groupings (continued)

Class of endpoint	Patient sets					
	SCR	TS	TSactive	RS	mITT	PPS
Descriptive statistics over time 
 
Lipid parameters
 
Renal parameters
 
Vital signs
 
 Freq. of patients with increase of serum creatinine shows a $\geq$ 2 fold increase from baseline and serum creatinine > upper limit normal		(OC-ROC) TG1, TG5				
Change from baseline over time - MMRM 
 
Lipid parameters
 
		(OC-ROC) TG1				
Shift in renal function category from baseline to last and minimum value on treatment		TG1				
Descriptive statistics 
 
Biomarkers
 
		(OC-ROC) TG1, TG5 (except DPP-4)				

[figure not shown]
SCR=screened set, RS=randomised set, mITT=modified intention-to treat set, PPS=per protocol set, TS=treated set, TSactive=treated set active; patient sets are defined in [Section 6.3](#)

OR=original results, OC=observed cases, OC-AD=observed cases-all data, OC-AD-BOCF=observed cases-all data and baseline observation carry forward, OC-ROC=observed cases-rescue observed cases, NCF=Non-completers considered failures. Handling of missing data is described in [Section 6.6](#). CFB: change from baseline, ANCOVA= Analysis of covariance, SMQ= Standardised MedDRA query, MMRM= Mixed model for repeated measures, HLGT, HLT= High level term, CEC= Clinical event committee

1 Present once at the end of the trial combining both DINAMO and DINAMO Mono data.

Table 6.3: 2 Patient sets analysed and treatment groupings for COVID-19 related outputs

[figure not shown]
Class of endpoint	Patient sets					
	SCR	TS	TSactive	RS	mITT	PPS
Premature discontinuation of trial medication or study	OR (TG1)					
Patient screened and study conduct	OR (TOTAL)					
Protocol deviations				(TG1)		
Demographic data		OR (TG1)				
Baseline efficacy variables		OR (TG1)				
Exposure to study medication		OR (TG1)	OR (TG6)			
Compliance data by visit		OR (TG1)	OR (TG6)			
Compliance with study medication by visit		OR (TOTAL)				
Freq. of patients and rate of treatment interruptions		(TG1)				
Summary of patients who completed, altered or missed HbA1c sampling at Week 26 visit					OR (TG1)	
Primary family of hypothesis - HbA1c (%) CFB - ANCOVA analysis-multiple imputation with washout approach using a specific COVID-19 imputation					OC-AD (TG1)	
Freq. of patients with COVID-19 intercurrent events					OC-AD (TG1)	
Freq. of patients and rate of AEs before and from the start of COVID-19 disruption		TG1	TG6			
Sub-population: SARS-CoV-2 infected patients 
 
Overall summary of AEs
 
Freq. of patients with AEs
 
Freq. of patients with AEs leading to treatment discontinuation
 
Freq. of patients with SAEs.
 
		TG1	TG6			

